3 DESIGN

This is a Phase 2 double blinded and placebo controlled randomized trial evaluating the efficacy and safety of camostat mesilate in adult subjects with PCR-positive, mild-moderate or COVID-19 infections.

Subjects will be randomized to receive either camostat mesilate + current Standard of Care (SOC) or SOC + placebo.

Study participants will be randomly assigned 1:1 to two tablets of oral camostat mesilate (200 mg) four times a day or current standard of care for 10 days.

Subjects in the SOC arm will receive a placebo. The total anticipated duration of the study for each patient is 28 days.

4 OBJECTIVES

4.1 Primary Objective

To evaluate the efficacy of oral camostat mesilate plus SOC compared with placebo plus SOC in reducing the AUC through day 10 of shedding of SARS-CoV2 virus in patients with mild-moderate COVID-19 disease.

4.2 Secondary Objectives

- 1. To evaluate the efficacy of oral camostat mesilate plus SOC compared with placebo plus current SOC in reducing the AUC up through day 28 of viral shedding of SARS-CoV-2 virus in patients with mild-moderate COVID-19.
- 2. To evaluate the efficacy of oral camostat mesilate plus SOC compared with placebo plus current SOC in reducing the duration of viral shedding of SARS-CoV-2 virus in patients with mild-moderate COVID-19.
- 3. To evaluate the efficacy of oral camostat mesilate plus SOC compared SOC plus placebo in reducing the duration of symptoms, hospitalizations or ED visits, or mortality in patients with mild-moderate COVID-19 disease.
- 4. To evaluate the proportion of individuals with a negative SARS-CoV2 RT PCR test on days 7, 14 and 28.

Confidential Page 17 of 42

- 5. To assess the safety and tolerability of camostat mesilate in this subject population.
- 6. To assess the development of antibodies against SARSCoV-2
- 7. To determine drug levels using the current dosing scheme.

5 SUBJECT POPULATION

5.1 Inclusion Criteria

All criteria must be confirmed as "YES":

- 1. Adults (18 to 80 years old inclusive)
- 2. Diagnosis of COVID-19 disease:
 - a. Presence of mild-moderate symptoms without signs of respiratory distress (as defined by SpO2 <=94% on room air, RR >=24, HR >=110), with FDA-cleared molecular diagnostic assay positive for SARS-CoV-2 within 72 hours from swab to the time of commencing informed consent. Mild-moderate disease is defined as having at least 20f the following symptoms that are of moderate or higher severity as scored on the COVID Outpatient Symptom Scale (COSS)::
 - i. Fever (>98.7F)
 - ii. Cough
 - iii. Shortness of breath
 - iv. Fatigue
 - v. Headache
 - vi. Body ache
 - vii. Joint pain
 - viii. Chest pressure
 - ix. Abdominal pain
 - x. Sore throat
 - xi. Nasal congestion
 - xii. Chills
 - xiii. Feeling hot or feverish
 - xiv. Runny nose
 - xv. Loss of taste
 - xvi. Loss of smell
 - xvii. Diarrhea
 - xviii. Nausea
 - xix. Vomiting
 - xx. Rash
 - b. The date of onset of the first of the above symptoms will be documented.
- 3. Subject or their legal representative understands the requirements of the study and provides written informed consent prior to undergoing any treatment-related procedures.
- 4. If male, subject must:

Confidential Page 18 of 42

- a. Be sterile (e.g., have had a vasectomy at least 6 months prior to Day 1 dosing), OR,
- b. Agree not to donate sperm during the study and for seven days following the last dose of study medication, AND,
- c. Agree to strictly adhere to the following contraceptive measures during the study and for seven days following the last dose of study medication:
 - i. Abstain from sexual intercourse.
 - ii. Use a condom during sexual intercourse with a female of child-bearing potential. In addition, the female partner must use another form of contraception (e.g. intrauterine device [IUD], diaphragm with spermicide, oral contraceptives, injectable progesterone, or subdermal implants).

5. If female, subject must:

- a. Be unable to bear children (have not had a period for ≥ 12 consecutive months, have had her uterus or ovaries removed, or have had a tubal ligation), OR,
- b. Must ensure that their male partner is incapable of fathering a child (e.g., has had a vasectomy at least 6 months prior to study entry), OR,
- c. If she is of childbearing potential will strictly adhere to the following contraceptive measures during the study and for seven days following the last dose of study medication:
 - i. Abstain from sexual intercourse, OR,
 - ii. Must ensure that her male partner agrees to use a condom during sexual intercourse and agree to use an approved method of contraception (e.g., IUD, diaphragm with spermicide, oral contraceptives, injectable progesterone, or subdermal implants).
- d. Agrees to stop breast-feeding prior to first dose of study drug and through seven days after completing therapy.
- e. Has a negative urine pregnancy test at screening.
- f. Has not had unprotected sexual intercourse within the past month.
- 6. When such testing is available, subject will be confirmed to be SARS-CoV2 infected using a rapid (<30 minute) SARS-CoV2 point-of-care test; if such a test is not available, this step of screening will be omitted.
- 7. Subject agrees to maintain home or other quarantine as recommended by the study physician, except to visit the study site as required by the protocol.
- 8. Subject agrees to take daily nasal swabs (anterior nares) for Day 1 to Day 10 and Day 14, 21, and 28 using the study provided material and bring these to their follow up visits on days 5, 10 and 28.
- 9. Subject agrees to record daily symptoms, temperature, oxygen saturation, and pulse using the study provided materials.
- 10. Subject agrees to return to the study site for follow-up visits on Day 5, 10 and 28. The study site will be staffed by trained healthcare providers wearing full personal protective equipment and study site equipment will be disinfected between patients according to the same protocols as a clinical setting. Subjects will be wearing masks, will be appropriately spaced, and the number of subjects assessed at each time will be limited.
- 11. Members of the same household may participate in the study as long as the inclusion and exclusion criteria are met.

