|---------------------------|---|--|--|--|
| | Secondary Endpoints | | | |
| | AUC of shedding of SARS-CoV-2 virus calculated using the RT-PCR measures of viral load from self-collected nasal swabs on days 1-10, 14, 21, and 28. Time until cessation of shedding of SARS-CoV-2 virus, defined as the time in days from randomization to the first negative RT-PCR result of self-collected nasal swabs that is followed by only negative results (i.e. no later positive results are observed). RT-PCR results from oropharyngeal swabs collected on Days 1, 5, 10 and 28 Clinical worsening of COVID-19 in symptomatic subjects (clinical worsening defined the development of respiratory distress or symptoms that require hospitalization) Adverse events AEs and clinical laboratory tests for systemic safety including hematology and clinical chemistry Mortality Development of antibodies to SARS-CoV-2 Time until resolution of symptoms (resolution of symptoms defined as absence of moderate or severe symptoms for at least 24 hours for those reporting moderate or severe symptoms at baseline). | | | |
| | 9. Drug level on day five, one hour after a dose taken on an empty stomach. | | | |
| Study Sites | Stanford University School of Medicine | | | |
| Planned Enrollment | 120 (60 in the camostat mesilate + SOC group and 60 in the placebo + SOC group) | | | |
| Study Population | Adults with confirmed SARS-CoV-2 who are experiencing mild-moderate symptoms | | | |
| Subject Entry Criteria | Inclusion Criteria (all questions must be answered YES) 1. Adults (18-80) 2. Diagnosis of COVID-19 disease: a. Presence of mild-moderate symptoms without signs of respiratory distress (as defined by SpO2 <=94% on room air, RR >=24, HR >=110), with FDA-cleared molecular diagnostic assay positive for SARS-CoV-2 within 72 hours from initial swab to the time of commencing informed consent: Disease is defined as having at least 2 of the following symptoms that are of moderate or higher severity as scored on the COVID Outpatient Symptom Scale (COSS): i. Fever (>98.7F) | | | |

Confidential Page 7 of 42

| • • | \sim 1 |
|-----|----------|
| 11. | Cough |
| | Cousii |

- iii. Shortness of breath
- iv. Fatigue
- v. Headache
- vi. Body ache
- vii. Joint pain
- viii. Chest pressure
- ix. Abdominal pain
- x. Sore throat
- xi. Nasal congestion
- xii. Chills
- xiii. Feeling hot or feverish
- xiv. Runny nose
- xv. Loss of taste
- xvi. Loss of smell
- xvii. Diarrhea
- xviii. Nausea
- xix. Vomiting
- xx. Rash

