7.1 Day 1 (PRE-DOSE)

- Obtain informed consent.
- Verify eligibility per the inclusion and exclusion criteria. (See Sections 5.1 and 5.2)
 - o Review and record medical history to ensure there are no exclusionary illnesses.
 - Review and record concomitant medications for possible prohibited medications. (See Section 6.7)
 - Record date of onset of symptoms
- If subject is female of child-bearing potential and meets inclusion criteria 5.e, obtain urine pregnancy test and proceed if result is negative.
- Measure and record vital signs (BP, HR, Temp, Resp).

Confidential Page 23 of 42

² If such symptoms are observed, administration should be discontinued.

- Collect and record SPO2 by Finger Sensor
- Perform Physical exam (may be done by the Principal Investigator or their designee)
- Collect oropharyngeal swab for virologic testing by RT-PCR and resistance testing.
- Collect blood samples for:
 - o Antibodies to SARS-CoV-2.
 - o Hematology and clinical chemistry laboratory analyses
 - Biobanking
- Perform subject randomization (via EDC) to establish treatment arm (camostat mesilate + SOC or SOC + placebo).
- Explain in home procedures for the study (self-sampling of nasal swabs, temperature, SPO2, completing the daily questionnaire).
- Provide supplies to research subject and review the calendar of return visits

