9.5 Stratification, Subgroup Analysis and Pooled Analysis

Following consent, those subjects meeting all entry criteria will be randomized in a 1:1 ratio

Treatment Arm: camostat mesilate + SOC

Control Arm: placebo + SOC

Randomization will be stratified by age (>=50 and <50 years old) and sex.

Members of the same household may participate in the study as long as the inclusion and exclusion criteria are met. Because this is a double-blind, placebo-controlled trial, subjects from the same household will be randomized just as any other subject.

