9.8 Primary efficacy analysis

To address our primary objective, the AUC SARS-CoV2 viral RNA levels during follow-up will be estimated using the linear trapezoidal method, and mean AUC levels compared between groups using a linear regression model regressing log(AUC) on treatment arm, site, age, and sex. If more than 3 sites are included to address the objectives, we will employ a mixed effects

Confidential Page 31 of 42

model, with a random effect for site. The test will be performed at the two-sided alpha = 0.05 level of significance.

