9.9 Secondary efficacy analyses

Time until shedding cessation will be compared between the two treatment arms using a Cox proportional hazards model adjusted for site, age, and sex. Time of cessation will be defined as the first negative result that is followed only by negative results. If more than 3 sites are included to address the objectives, we will employ a stratified Cox model, stratified by site, allowing each site to have its own baseline hazard. The hazard ratio for shedding cessation will be estimated, along with its 95% confidence interval, from a Cox proportional hazards model. If the proportional hazards assumption is not met, we will consider an extended Cox model that relaxes the proportional hazards assumption

The distribution of shedding cessation will be estimated using the Kaplan-Meier method, and Kaplan-Meier curves will be presented for each treatment arm. Time to shedding cessation at the end of the study period along with 95% confidence intervals will be presented for each treatment arm.

The distribution of time to resolution of symptoms will be estimated using the Kaplan-Meier method, and Kaplan-Meier curves will be presented for each treatment arm. Time to resolution of symptoms at the end of the study period along with 95% confidence intervals will be presented for each treatment arm. The hazard ratio for resolution of symptoms will be estimated, along with its 95% confidence intervals, from a Cox proportional hazards model. Time to resolution of symptoms will be determined by analysis of daily questionnaires (see Appendix A2). Resolution of symptoms requires that symptoms are mild or absent for at least 24 hours. The analysis of symptom resolution will be conducted on the symptomatic ITT population, i.e. participants who report moderate or severe symptoms at baseline. These analyses will be repeated in a second analysis considering only respiratory symptoms, i.e. fever, cough, shortness of breath, sore throat, headache, and nasal congestion/runny nose. This analysis will be performed on the subset of patients who report moderate or severe respiratory symptoms at baseline.

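### Time since symptom onset is uncapped at entry and named in no stratum, efficacy model or subgroup, so avoidable variation stays in log(AUC) and power is lost in the shedding and symptom-resolution models.

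*Combined protocol and SAP*

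**What the plan says.** **Entry.** Section 5.1 requires at least two listed symptoms of moderate or higher severity and a molecular test "positive for SARS-CoV-2 within 72 hours from swab to the time of commencing informed consent". The synopsis has nearly the same rule but refers to the initial swab. Neither the inclusion nor the exclusion list sets a maximum time since first symptom.

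**Collection.** The onset date is captured under 5.1 item 2b ("The date of onset of the first of the above symptoms will be documented") and again before dosing in section 7.1 ("Record date of onset of symptoms").

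**Design and analysis.**
- Section 9.5: "Randomization will be stratified by age (>=50 and <50 years old) and sex". The heading of 9.5 mentions subgroup analysis, but the section specifies none.
- Section 9.8, primary: a "linear regression model regressing log(AUC) on treatment arm, site, age, and sex".
- Section 9.9, shedding cessation: a "Cox proportional hazards model adjusted for site, age, and sex". The synopsis lists age and sex only. The synopsis endpoint is "defined as the time in days from randomization to the first negative RT-PCR result", with no later positive.
- Section 9.9, symptom resolution: "The hazard ratio for resolution of symptoms will be estimated, along with its 95% confidence intervals, from a Cox proportional hazards model". No covariates are named.

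Onset date appears in none of these. Day 1 viral load is not a covariate either, so nothing in the models stands in for illness stage.

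**The concern.** COVID-19 in outpatients is usually self-limiting. Viral AUC over the next ten days, time to the last positive swab and time until symptoms settle should all depend on how far the illness has run at entry. The clock for these endpoints starts at Day 1 or randomisation, so differences in stage enter the outcome directly.

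Randomisation balances stage on average. What is lost is efficiency. In the linear model for log(AUC), an omitted prognostic covariate enlarges the residual variance, and a chance difference in stage between arms passes into the estimate. In a Cox model the mechanism differs: the hazard ratio is attenuated toward 1, and power falls for that reason rather than through a larger standard error. The trial has no spare power to absorb this, and the variable needed is already collected.

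**Working it through.** **Inputs.** Section 9.2 gives 60 per arm, a standardised effect of 0.5, a two-sided final alpha of 0.04999 and a claimed power of 80%. It names both a log-rank test and a two-sample t-test. The t-test is used here, because no hazard ratio or event count is given for the log-rank reading. The share of log(AUC) variance explained by onset time beyond age and sex, R², is not in the documents. The values 5%, 10% and 20% are assumed.

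**Step 1: the plan's own figure.** The noncentrality is 0.5 × √(60/2) = 2.739. The normal approximation gives Φ(2.739 − 1.960) = 78.2%, near the stated 80%. The exact t-test gives 77.5%, and 80% power would need 64 per arm.

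**Step 2: gain from adjustment.** Taking 0.5 in units of the total SD, the adjusted effect size is 0.5/√(1 − R²). The equivalent sample-size factor is 1/(1 − R²).

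| Assumed R² | Adjusted effect size | Power, 60 per arm | Equivalent sample size |
|---|---|---|---|
| 0 | 0.500 | 77.5% | 1.00 |
| 5% | 0.513 | 79.6% | 1.05 |
| 10% | 0.527 | 81.7% | 1.11 |
| 20% | 0.559 | 85.9% | 1.25 |

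Moving from 118 to 117 residual degrees of freedom changes these powers by no more than about 0.01 percentage point.

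**Step 3: the other reading of 0.5.** If 0.5 was set on an SD free of onset variation, the unadjusted effect size is 0.5 × √(1 − R²). Leaving onset time out then gives 75.4%, 73.1% or 68.1% at the same R² values.

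**Step 4: chance imbalance.** The standard error of the between-arm difference in mean onset time is √(2/60) = 0.183 SD. An imbalance of that size shifts the unadjusted difference in log(AUC) by √R² × 0.183, which is 0.041, 0.058 or 0.082 SD for the three R² values, against a target effect of 0.5. This is the same variance loss as in Step 2, seen in a single trial, and is not an additional cost.

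**Step 5: what an interaction could show.** A median split leaves about 30 per arm in each half. The standard error of the difference between the two treatment effects is √(4/30) = 0.365 SD. If the effect were 0.5 SD in one half and zero in the other, z = 0.5/0.365 = 1.37 and power is about 28%.

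**Not computed.** No figure is given for the Cox models. The factor 1/(1 − R²) does not carry over to them, and the documents give no event rates or prognostic strength.

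**The case against.** **Entry is not wide open in practice.** Two symptoms of at least moderate severity, a positive test within 72 hours, and a rapid confirmatory test where available all narrow the spread of onset times. That stands as a limit on size, but none of these caps onset. The swab wording that differs between 5.1 and the synopsis should be reconciled. It does not show that late repeat positives were meant to qualify.

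**The plan is unfinished and has general clauses.** Section 9 defers full detail to a later SAP, and the imputation model in 9.9 takes in all baseline characteristics. A reader might infer that onset date is used nowhere, which goes too far: it may enter the imputation and the baseline summaries. Neither adjusts the treatment comparison, however, and the covariate lists are already written without it.

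**The gain is assumed and could be small.** This stands. At 5% it is 2.1 points of power. Onset is a recalled date for the first of twenty symptoms, so recall error would lower R². Day 1 viral load from the nasal swab is a more direct measure for the AUC and would absorb part of the gain.

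**Two stronger readings are tempting.** One is that every efficacy endpoint suffers. Noise from viral or symptom decline is not shown for mortality, clinical worsening, hospitalisation or emergency visits. The other is that a subgroup by duration would separate a null result from late treatment. Step 5 shows that it would not.

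**Conclusion.** The point holds for log(AUC), shedding cessation and symptom resolution. Entry has no cap on time since onset, and the recorded date is named in no stratum, efficacy model or subgroup. For the primary endpoint the cost is avoidable residual variance and uncorrected chance imbalance. For the two Cox models it is attenuation of the hazard ratio and loss of power. The validity of the tests is not in question: type I error is unaffected and no systematic bias between arms is introduced.

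The only quantified gain is on the primary endpoint: 2.1, 4.2 or 8.4 points of power over 77.5%. It is illustrative. It rests on the assumed R², on 0.5 being in total-SD units, and on no viral baseline being in the model. The direction for the Cox models is sound if onset time is prognostic for those endpoints, but its size cannot be derived from the documents. The change is worth making because it is nearly free.

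**What to change.** In sections 9.8 and 9.9, and in the synopsis to match, pre-specify before unblinding the number of days from symptom onset to randomisation, as a continuous covariate, in the log(AUC) regression and in the Cox models for shedding cessation and symptom resolution. State that the adjusted hazard ratios are conditional on this covariate and so differ in meaning from marginal ones. If Day 1 viral load is also added to the AUC model, keep both and expect a smaller contribution from onset time.

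A treatment-by-duration estimate may be listed in 9.5 if labelled exploratory and descriptive. It should not be presented as able to explain a null result.

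The cost is wording in the protocol and SAP and one degree of freedom per model. No new data are needed, and entry criteria need not change.

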5.2 Exclusion Criteria

All criteria must be confirmed as "NO":

Confidential Page 19 of 42

1. Subject has a concomitant bacterial respiratory infection, as defined by positive respiratory culture

NOTE: Subjects on empirical antibiotic treatment for possible but unproven bacterial pneumonia, but who are positive for SARS-CoV-2, are allowed in the study.

- 2. Previous use of antiviral drugs that may be active against COVID-19.
- 3. Subject is using adrenocorticosteroids (except topical or inhaled preparations or oral preparations equivalent to or less than 10 mg of oral prednisone) or immunosuppressive or immunomodulatory drugs (e.g., immunosuppressants, anticancer drugs, interleukins, interleukin antagonists or interleukin receptor blockers).

NOTE: Treatment of study participants following institutional COVID-19 treatment policies or guidelines, including the use of immunomodulatory medications, is permitted. This excludes treatment with agents that have the potential for direct antiviral activity, including convalescent plasma and NO, and co-enrolment into other clinical studies that evaluate investigational agents for COVID-19.

- 4. Subject has gout, a bleeding disorder, or a serious chronic disease (e.g., human immunodeficiency virus [HIV], cancer requiring chemotherapy within the preceding 6 months, moderate or severe hepatic insufficiency and/or unstable renal, cardiac, pulmonary, neurologic, vascular, or endocrinologic disease states requiring medication dose adjustments within the last 30 days).
- 5. Subject uses an anticoagulant medication including heparin, coumadin, a factor Xa inhibitor (xarelto, apixaban) or a thrombin inhibitor (Pradaxa). Aspirin is not an indication for exclusion
- 6. Has previously received camostat mesilate within the past 30 days.
- 7. Has renal insufficiency requiring hemodialysis or continuous ambulatory peritoneal dialysis (CAPD).
- 8. Has liver impairment greater than Child-Pugh A.
- 9. Has a history of alcohol or drug abuse in the previous 6 months.
- 10. Has a psychiatric disease that is not well controlled where controlled is defined as: stable on a regimen for more than one year.
- 11. Has taken another investigational drug within the past 30 days.
- 12. Is deemed by the Investigator to be ineligible for any reason.

